employing a low dose regimen of relatively short duration. The risk of retinal damage is very low even with the much higher doses used for prolonged treatment of rheumatoid disorders, with the risk increasing if treatment is continued for longer than 5 years or if the cumulative dose is high. In this study, the dose of 100 mg twice weekly averages to a daily dose of less than 0.5 mg/kg for a 70 kg patient, and the duration of treatment will be less than 5 years. Therefore, a second ophthalmological examination will be done at the end of treatment rather than 5 years. Each participating institution will have their own standard practices established by ophthalmology departments based on the guidelines shown in Table 7.

| | Table 7. Recommendations of the American Academy of Ophthalmology on screening patients | | |
|--|---|--|--|
| treated with chloroquine and hydroxychloroquine [78]. | | | |
| Timeline | Baseline examination within first year of use | | |
| | Annual screening after 5 yrs of use | | |
| Recommended So | creening Procedures | | |
| Ocular examination | Dilated retinal examinations are important for detection of associated retinal disorders, but should not be relied on for screening (low sensitivity). | | |
| Automated visual field | White 10-2 threshold testing. Interpret with a low threshold for abnormality, and retest if abnormalities appear. | | |
| In addition, if availa | ble, perform one or more of the following objective tests | | |
| SD-OCT | Rapid test that can be done routinely; can show abnormalities very early, even before field loss | | |
| mfERG | Valuable for evaluation of suspicious or unreliable visual field loss; may show damage earlier than visual field testing | | |
| FAF | May validate other measures of toxicity; can show abnormalities earlier than field loss | | |
| Not Recommende | d for Screening | | |
| Fundus photography | Recommended for documentation, especially at baseline, but not sensitive for screening | | |
| Time-domain OCT | Insufficient resolution for screening | | |
| Fluorescein angiography | Use only if corroboration of pigmentary changes is needed | | |
| Full-field ERG | Important for evaluation of established toxicity, but not for screening | | |
| Amsler grid | Use only as adjunct test | | |
| Color testing | Use only as adjunct test | | |
| EOG | Questionable sensitivity | | |
| Abbreviations: EOG = electro-oculogram; FAF = fundus autofluorescence; mfERG = multifocal electroretinogram; SD-OCT = spectral domain optical coherence tomography. | | | |

The recommendation in the product labeling for hydroxychloroquine for ophthalmological examination before and at 3 month intervals during treatment for lupus or rheumatoid arthritis is considered outdated and leads to unnecessary health care costs (50), and less frequent examinations are recommended in the recently revised guidelines of the American Academy of Ophthalmology (78).

Participants will be questioned at each visit about specific eye symptoms, such as reading and seeing difficulties, missing objects or parts of objects, missing or blacked out areas, blurred vision, halos around lights, photophobia, light flashes or streaks. Evidence of ophthalmic complications of hydroxychloroquine, although unlikely, will be reason for discontinuing the drug. The patient may then be treated by phlebotomy.

- V3 Date: 25FEB2020
- 4. Neuromuscular symptoms. Participants will be questioned at each visit regarding neuromuscular symptoms such as sensory changes and weakness, and examined for sensory changes, depression of deep tendon reflexes and loss of muscle strength, which are reported side effects of hydroxychloroguine.
- 5. Precautions for children. Participants taking hydroxychloroquine will be warned to keep the medication out of the reach of children.
- 6. Harmful exposures. Participants will be advised to avoid exposure to ultraviolet light (sunlight, tanning parlors, etc.) and alcohol, smoking, iron supplements, estrogens or other substances known to exacerbate PCT. This is part of standard clinical advice given to participants with PCT.
- **4.M. Efficacy.** Efficacy will be assessed primarily by laboratory results. Information on symptoms and signs will also be recorded.
 - 1. Laboratory Tests

The primary measures of efficacy will be plasma total porphyrin concentration, the plasma fluorescence emission spectrum at neutral pH, and urinary porphyrins (total as well as fractionated). The following will be measured at each visit.

- Plasma total porphyrins
- Plasma fluorescence emission spectrum at neutral pH
- Urinary porphyrins (total, and separation of individual porphyrins by high performance liquid chromatography-HPLC)
- Plasma and urinary exosomal ALAS1 mRNA

The following will be done on an optional research basis based on preliminary results from the interim analysis (45):

- Samples will be collected for measurement of urinary iron excretion will be done on a research basis, with precautions to avoid contamination, at baseline and at 1, 3 and 6 months of treatment by graphite furnace atomic absorption mass spectroscopy or inductively coupled plasma mass spectrometry (80, 81).
- Serum HCV RNA quantitative will be determined on an optional basis before and at 1, 2, 3, and 6 months (total = 5) in participants with PCT and hepatitis C on either therapy.

2. Cutaneous manifestations

Symptoms related to PCT, such as appearance of new blisters or milia, as well as other symptoms that might result from concomitant conditions such as hepatitis C or from treatment, will be recorded on CRFs at each visit.

At each visit, the number of new lesions, especially blisters and milia, will be counted. The backs of both hands will be photographed, if possible, and kept in the participants study chart to document any new lesions and improvement in the number of lesions.

Pain may occur as a result of cutaneous lesions, but is otherwise not a prominent or characteristic feature of PCT. If participants have pain or other symptoms that can be graded, the following scale will be used. This information will be recorded on CRFs.

| Scale | Descriptions for pain and other symptoms |
|----------|---|
| Absent | No pain |
| Mild | Awareness of pain but easily tolerated. |
| Moderate | Pain not easily tolerated and interferes with usual activities. |
| Severe | Pain incapacitating and prevents usual activities. |

4.N. Concomitant therapy. Drugs other than hydroxychloroquine will not be allowed in this study for treatment of PCT. Other drugs will be permitted if needed for symptomatic relief or other medical conditions, and will be recorded at the time of each study visit. Estrogens will be stopped until a remission is achieved (30). Iron-containing preparations will be discontinued. Participants will be recommended to stop use of alcohol and tobacco, as is standard for management of PCT. There will be no dietary restrictions. Compliance with these recommendations will be monitored during the study.

4.O. Adverse experiences. At the time of each visit it will be determined whether any adverse experiences have occurred. The participants will be questioned in a general way and no specific adverse symptoms will be suggested, except in regard to the symptoms to be recorded on the CRFs or symptoms that are of particular importance in the clinical management of an individual patient. Any clinical adverse experiences that have occurred will be recorded on the CRFs, and a judgment made regarding whether or not the adverse experience was related to study treatment.

Any serious adverse experience (SAE), including death, due to any cause and occurring during the course of this investigation, whether or not related to the study treatments or procedures will be reported immediately to the Institutional Review Board (IRB) at the site, the IRB at UTMB, the Clinical Research Center at UTMB and the site, if required, and the US Food and Drug Administration.

A SAE with respect to clinical experience includes any experience that is fatal or life-threatening, is permanently disabling, or either requires or prolongs inpatient hospitalization.

4.P. Patient withdrawal. Every reasonable effort will be made to keep participants in the study. If a patient wishes to leave the study or is removed by the PI, a complete final evaluation will be performed. A narrative description of the reason(s) for withdrawal from the study will be recorded in the source documents.

The following are justifiable reasons for removing a patient from the study:

- 1. Development of a study exclusion criterion, as previously listed
- 2. If continuing the study presents an unacceptable risk or discomfort to the patient.
- 3. Violation of the study protocol.
- 4. The patient is uncooperative or noncompliant in study-related observations or in administration of study medication.
- 5. Consent is withdrawn.
- 6. The study is terminated.

4.Q. Treatment failure or intolerance. Participants who fail therapy are expected to be few. Participants who fail or develop contraindications to the treatment assigned will be switched to the alternate treatment and continue to be followed in the study. Reasons for changing treatment will be recorded within the study. Participants who relapse and require retreatment will also remain in the trial. Data from second or subsequent treatments will be collected, but analyzed separately from data obtained during the first treatment in the trial. Rare patients who are not eligible for either treatment will continue to be followed, anticipating that their eligibility may change and treatment will be possible. There is no specific standard-of-care as to when participants are switched to alternate therapy, because failure of treatment is highly unusual and poorly documented with either type of therapy, except when there is noncompliance or other reasons for not completing the therapeutic procedures as planned. The study will provide important new information on patients who need to change therapy for PCT. Participants also have the option of withdrawing from the study at this or any other time.

V3 Date: 25FEB2020

4.R. Data analysis and statistical considerations. This was originally designed as a randomized noninferiority clinical trial, with inclusion of participants who could not be randomized in a substudy, but with the same treatment and follow up for all participants. We had anticipated that 90% of participants could be randomized, and the intent was to include only randomized participants in the noninferiority analysis. A planned interim analysis, which has been published (45) found that more than half the participants could not be randomized due to medical reasons or patient preference; therefore the interim data was analyzed for the randomized participants and for all participants. Although the treatments appeared equivalent in terms of time to remission, statistical significance was not achieved. Therefore, after formation of the Porphyrias Consortium (PC), the study was continued as a PC study with the goal of enrolling enough participants for a statistically significant result. Based on the interim analysis, the PC investigators identified additional value in continuing this study to enroll a larger number of participants. 1.) Like the PC Longitudinal Study (LS), PC7201, this study enrolls participants with well documented PCT who are characterized for all of the known susceptibility factors. which are multiple but different for individual participants. But unlike the LS, this study carefully documents treatment response and remission, and allows assessment of treatment response and durability as related to specific, multiple susceptibility factors, some of which may change over time. 2.) This study will allow examination of the importance of newly-identified or postulated susceptibility factors, not only for contributing to development of PCT but for affecting treatment responses. 3.) This study is developing for the first time reference information on time to remission for phlebotomy, presently for comparison with hydroxychloroguine. But additional treatment arms may be added to the study as new therapeutic approaches are developed in the future.

The study will continue as a more pragmatic study relevant to clinical practice, with assignment to treatment based on uniform criteria and randomization only of participants eligible for both treatments, to avoid unnecessary bias. Therefore, it will be a two-group study with no substudy. A descriptive approach to data analysis will be employed, with clinically relevant comparisons of the two treatments, rather than a noninferiority analysis.

Inclusion of all available participants rather than just the minority that can be randomized has a number of advantages. Participants eligible for both treatments (and therefore eligible for randomization) might respond differently than those who are not, since some of the reasons that make participants ineligible for one treatment relate to certain susceptibility factors and to prior treatment experience. Exclusion of a majority of participants from treatment comparisons also would make the study less pragmatic and less clinically relevant. In the interim analysis, randomized and nonrandomized participants did not differ in terms of clinical and demographic

features, but such important comparisons would be more meaningful with a larger number of participants. In the amended study, participants who are eligible for both treatments are to be randomized as a method for choosing between treatments that is needed in the study to avoid bias, but not as a study design feature. Bias might arise, for example, from existing site-specific treatment preferences.

A total of at least 100 participants will be assigned, based on medical criteria, preference, or (if eligible for both treatments) by randomization, to one of these standard treatment groups. CRFs will be completed for each patient, including porphyrin levels, and data entered into the study database. This database is designed by and housed at the Data Management and Coordinating Center (DMCC) at the University of South Florida in Tampa. The DMCC is supported by the NIH Rare Diseases Clinical Research Network and serves as the secure repository for de-identified data for all consortia in the Network. Upon approval from the UTMB IRB and the Porphyrias Consortium DSMB, data from patients previously enrolled in this study at UTMB starting in 2006 before the study was a RDCRN study will be entered into the database. Subjects will be contacted to give their consent for this data transfer to the DMCC and storage in a federal data repository. For subjects who are now deceased consent will be obtained from next of kin. For subjects who cannot be re-contacted or where the next of kin cannot be re-contacted, approval of the UTMB IRB and the Porphyrias Consortium DSMB will be sought for this data transfer. Transferring this previously collected de-identified data is not expected to cause any increased risks to subjects. Data will be verified and edited where necessary for completeness and consistency by comparison with source documents. Study outcomes, such as time to achieving biochemical endpoints, will be determined from this data. As was found in the interim analysis, assignment to the two groups is unlikely to be equal, and more will be assigned to phlebotomy than to hydroxychloroquine. As in the interim analysis, times to achieving measures of remission are not expected to be substantially different for the two treatment groups. Effects of multiple susceptibility factors and other clinical and demographic features on treatment response and durability will be further examined. Outcome measures such as time to remission will be compared using Cox proportional models to study the effects of susceptibility factors on the hazard ratio to compare the two treatments. All patients who start treatment will be included in the analysis. Safety measures will be compared more descriptively where the adverse effects of each type of treatment are different.

The following susceptibility factors for PCT will be summarized and tabulated, and examined for balance across treatment groups. Differences in response based on susceptibility factors will be examined by multivariate analysis. The following susceptibility factors will be emphasized in this analysis:

- 1. Alcohol use (presence or absence)
- 2. Smoking (presence or absence)
- 3. Estrogen use (presence or absence)
- 4. Hepatitis C (presence or absence)
- 5. HIV (presence or absence)
- 6. UROD mutations (presence or absence)
- 7. HFE mutations (presence or absence of C282Y and H63D, and specific genotype combinations)

The analysis regarding susceptibility factors will take into consideration that some (e.g. homozygotes for HFE mutations with high ferritin levels) are medical reasons for assignment to one treatment group and not the other. We recognize that because the number of participants in subgroups based on susceptibility factors or combinations of susceptibility factors will be

relatively small, and it may not be possible to detect or exclude statistically significant differences for all susceptibility factors. The data is expected to support continuing this study with larger numbers of participants, or to suggest whether other studies should be designed to clarify the effects of these factors on treatment response and durability.

Additional modeling will assess factors affecting the frequency of recurrence and seasonality effects using logistic regression modeling and log-rank testing, respectively.

Sample Size and Power. A sample size calculation was performed to assess power for a study assessing the effect of factors on time to remission. Extremely common or rare factors are detected with 80% power for 90 subjects (and some dropout) when the hazard ratios are 2.3 (alcohol consumption and UROD deficiency), 2.2 (smoking history), 3.2 (estrogen usage), 2.0 (hepatitis C), and 1.9 (HFE mutations). In summary, this approach for times to remission leads to a sample size of approximately 50 subjects per group. All analyses were conducted in nQuery Advisor Version 5.0 (Janet Elashoff (2002); nQuery Advisor Version 5.0 User's Guide. Los Angeles, CA).

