This study was initially conceived as a randomized noninferiority study, with inclusion of nonrandomized participants to be treated and followed in a substudy. But as described above, an interim analysis found that more than half the participants were either not medically eligible for both treatments or preferred to choose their treatment, and therefore were not eligible for randomization (45). The results found no major demographic or clinical differences between randomized and nonrandomized participants, and treatment responses were also similar. For reasons noted above, the study will continue with inclusion of all treatment-eligible participants as a more pragmatic study relevant to clinical practice, with assignment to treatment based on uniform criteria and randomization only of participants eligible for both treatments, to avoid unnecessary bias. A descriptive approach to data analysis will be employed, with clinically relevant comparisons of the two treatments. A larger number of subjects will allow assessment of effects of susceptibility factors on treatment response and durability.

Study visits are scheduled at 2-4 week intervals to document achieving a target ferritin concentration in subjects treated by phlebotomy, and for both treatments achieving a normal plasma porphyrin concentration. Visits may be less frequent than 2-4 weeks early in the course of treatment if, for example, during a course of phlebotomies the serum ferritin is still well above the target concentration, or if after phlebotomies are complete or during hydroxychloroquine treatment the plasma porphyrin concentrations are still quite high and not yet approaching normal.

Once a normal plasma porphyrin concentration is achieved visits will then be scheduled at 4-8 week intervals to document achieving the additional treatment outcomes and complete remission of PCT. Less frequent visits may be scheduled if these outcomes are not yet approaching normal, although the time course of improvements in these outcome parameters can be difficult to predict. The expected order of achieving these outcomes with each treatment is as follows:

- 1. Phlebotomy only: Target ferritin (<20 ng/mL) expected ~2 weeks after the last phlebotomy. (This requirement can also be met by a ferritin of 25 ng/mL on the same day as the last phlebotomy.)
- 2. Normal plasma porphyrin concentration
- 3. Absence of a fluorescence peak in plasma at neutral pH
- 4. Normal urine total porphyrins

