- 5. Normal pattern of urine porphyrins by HPLC

How quickly each of these targets and outcomes will be achieved will vary greatly among patients. Therefore, levels need to be followed closely to anticipate when visits are needed to document treatment outcomes. If less frequent visits than recommended are contemplated, site investigators should review laboratory results within 3 days of receiving the reports and determine when the next visit and the next set of tests should be done in order to document all primary and secondary outcomes.

To be considered an evaluable outcome, time to achieving each of the study outcomes listed above (e.g. time to achieving a normal plasma porphyrin level) will be documented by an abnormal finding (e.g. a high plasma porphyrin level) followed by normalization of that finding

(e.g. achieving a normal plasma porphyrin level) within a specified time interval, which is referred to as the *documentation window* for achieving that outcome. That interval/documentation window will be 4 weeks for achieving a normal plasma porphyrin concentration, and 8 weeks for achieving the later biochemical outcomes. Therefore, a single missed visit that is not within one of these windows should not lead to a missed verification of a treatment outcome.

The following study practices are recommended to document the major study outcomes:

- 1. A phlebotomy patient should return every 2 weeks after the ferritin falls to 60 ng/mL, in order to either 1) document a ferritin of 25 ng/mL on the day of the last phlebotomy, or if serum ferritin was not measured on the day of the last phlebotomy, 2) to document a ferritin level of <20 ng/mL ~2 weeks after the last phlebotomy.
- 2. Once the plasma porphyrin level drops to less than ~4 mcg/dL, this test should be repeated biweekly to ensure that, even if a visit is missed, normalization is captured within the 4-week documentation window, which will properly document time to this primary treatment outcome.
- 3. After the plasma porphyrin concentration is normal (<0.9 mcg/dL), visits should be scheduled at 4 week intervals until the other outcomes are achieved. If visits are missed intermittently, this will still allow capturing a change from abnormal to normal within an 8-week documentation window.

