The treatment outcomes for this study are documentation of times to normalization of several porphyrin laboratory measurements, which occur in sequence at different times during the Treatment Phase. Study performance will be assessed by whether or not primary study outcomes are documented within specified time windows. *Documenting the time to each outcome requires an abnormal result followed by a normal result within a specified time window.* The windows of documentation for each treatment outcome are shown in Table 5. Experience to date indicates that these outcomes are usually achieved in the order shown. All outcome measures may not be documented in all patients, but with four rather than one outcome measure it is more likely that each patient will achieve documentation of at least some of these outcomes.

| Table 5. Treatment outcomes and windows for documentation | | |
|---|------------------|--|
| Treatment Outcomes | Windows for | |
| | Documentation of | |
| | Outcomes | |
| Normal plasma porphyrin level | 4 weeks | |
| Disappearance of plasma fluorescence peak | 8 weeks | |
| at ~619 nm | | |
| Normal urine total porphyrins | 8 weeks | |
| Normal pattern of urinary porphyrins | 8 weeks | |

Time to achieving each of these treatment outcomes and the location of each of these outcome windows in time during the Treatment Phase will vary among individual participants. For this reason, regular visits should be scheduled based on these windows, and less frequent visits scheduled only after examination of the most recent laboratory results.

4.H. End of treatment. The maximum duration of treatment will be 24 months, but is expected to be shorter for most participants. Treatment by phlebotomy will end when the target ferritin value is reached (≤20 ng/mL, or ≤25 ng/mL on the day of the last phlebotomy). Therefore, it is advantageous, if possible, to obtain ferritin measurements on the days of phlebotomy. Porphyrin levels will start to decrease, but will not be normal when phlebotomies are ended. Therefore the Treatment Phase of the study extends beyond the last phlebotomy until all treatment outcomes are documented. Factors that may lengthen the duration of phlebotomy treatment include marked iron overload, some loss of venous access and difficulty adhering to treatment visits.

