4.L. Safety. Safety parameters are based on known side effects of both treatments and include suggestions of the UTMB IRB and the FDA CDER. Participants will be evaluated at the beginning of the study to ensure that they meet the entry criteria and are informed about risks and precautions. They will then be monitored at study visits for assessment of safety. Close monitoring of hemoglobin or hematocrit may occur as a part of standard treatment by phlebotomy. This is not the case for hydroxychloroquine, because initiation of treatment in clinical practice requires only one visit to prescribe the drug, and continued visits are not needed to administer treatment. Therefore, safety monitoring will be as good or better than in clinical practice.

1. History and physical examination

History and physical examination (including height and weight) will be performed at the beginning and end of the study. Results will be recorded on CRFs.

Schedule of Events

| | Baseline (Day -60 to Day -1) | Treatment Period (including all treatment outcomes) | Follow Up Period (to monitor for recurrence) |
|---|------------------------------------|---|--|
| Visit frequency | One visit or as needed | Every 2-4 weeks until plasma porphyrin concentration normal, then every 4-8 weeks | Every 3-6 months |
| Medical History and physical examination | Х | | Annually & End of study |
| Documentation of PCT & porphyrin testing- urine total porphyrins, plasma total porphyrins*, erythrocyte protoporphyrin, UROD mutation testing, erythrocyte UROD, urine ALA & PBG, fecal porphyrins (optional) | х | | |
| Lab assessment for susceptibility factors- serum anti- HCV (with follow up HCV RNA if positive), serum anti- HIV, HFE mutation testing | X | | |
| Screening Lab tests- serum ferritin, complete metabolic panel%, CBC with Diff, hemoglobin A1C, Erythrocyte glucose-6-phosphate dehydrogenase screening, PT, aPTT, serum iron & TIBC | Х | | |
| Alcohol & Tobacco Use Questionnaires | X | | |
| History of Estrogen Use (type, dose, duration, how recent) | Х | | |
| PCT Symptom Assessment | Х | Х | Х |

| Liver ultrasound and/or liver biopsy (if clinically indicated) | Х | | |
|---|---|----------|---|
| Ophthalmologic Evaluation (only for HCQ participants) | Х | Annually | |
| Plasma and urine (24 hour or spot sample) total porphyrins, quantified & plasma porphyrins fluorescent peak# | | X | X |
| Urine pregnancy test | Х | X | |

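### A remission time is evaluable only inside a 4- or 8-week window, yet Section 4.R puts every treated patient into Cox models and gives no event date for a remission first seen outside it

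*Combined protocol and SAP*

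**What the plan says.** Section 4 (Research design and methods) sets the condition: "To be considered an evaluable outcome, time to achieving each of the study outcomes listed above" must be shown by an abnormal finding followed by its normalization inside a documentation window. It then fixes the lengths: "That interval/documentation window will be 4 weeks for achieving a normal plasma porphyrin concentration, and 8 weeks for achieving the later biochemical outcomes". Section 4.G repeats the condition ("Documenting the time to each outcome requires an abnormal result followed by a normal result within a specified time window") and gives the windows a second use: "Study performance will be assessed by whether or not primary study outcomes are documented within specified time windows".

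Section 4.R plans Cox proportional hazards models for outcomes such as time to remission and commits to including all patients who start treatment. On dating, it says only that times to the biochemical endpoints will be obtained from the collected data. It gives no event-date or censoring rule.

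On visit spacing:
- **Primary outcome.** Once plasma porphyrin falls below about 4 mcg/dL, "this test should be repeated biweekly to ensure that, even if a visit is missed, normalization is captured within the 4-week documentation window".
- **Later outcomes.** The recommended practices in Section 4 call for visits 4 weeks apart. Earlier in the same section, "visits will then be scheduled at 4-8 week intervals to document achieving the additional treatment outcomes and complete remission of PCT", with less frequent visits possible although "the time course of improvements in these outcome parameters can be difficult to predict". The Schedule of Events has "Every 2-4 weeks until plasma porphyrin concentration normal, then every 4-8 weeks".

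The Background reports that the primary time was evaluable in 30 of 48 interim patients (17 phlebotomy, 13 hydroxychloroquine). It attributes the shortfall mostly to missed study visits near remission, and says missed visits were commoner with phlebotomy.

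**The concern.** Two instructions in the plan meet on the same patient and do not agree. Take someone whose last abnormal test and first normal test are ten weeks apart. Section 4 says this patient has no evaluable time. Section 4.R says the patient is in the analysis. The analyst could drop the patient (against 4.R), censor at the last abnormal test (treating a known remission as not seen), date the event at the first normal test, or date it somewhere in between. The choice would be made with the data in hand.

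The hazard ratio between treatments and the times to remission are the main product of the study; 4.R describes the phlebotomy times as first-of-their-kind reference information. Both depend on the missing rule. The treatment comparison is most exposed if visits are missed unequally by arm, which is what the interim reported.

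**Working it through.** **1. The plan's own figure.** 17 + 13 = 30, and 30/48 = 62.5%, in line with the roughly two thirds quoted in the Background conclusions. Not evaluable: 18/48 = 37.5%.

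**2. How many of the 18 were remissions seen outside the window?** Call this k. Missed visits near remission suggest that some were. The Figure 2 caption, however, describes the 30 analysed patients as those who reached a normal plasma porphyrin, which taken literally gives k = 0. So k lies between 0 and 18.

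**3. Precision lost by excluding known remissions.** For a fixed arm split, SE(log HR) is proportional to 1/√events, so the ratio of SEs is √(known remissions / evaluable remissions). Earlier patients number 52 (Background, Study initiation) or about 40 (100 minus the roughly 60 still to enrol, Section 4.D). The first two rows assume no loss among later patients.

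| Scenario, N = 100 | k = 0 | k = 10 | k = 18 |
|---|---|---|---|
| Loss in 40 earlier patients only | √(85/85) = 1.00 | √(93.3/85) = 1.048 | √(100/85) = 1.085 |
| Loss in 52 earlier patients only | √(80.5/80.5) = 1.00 | √(91.3/80.5) = 1.065 | √(100/80.5) = 1.115 |
| Interim-like loss in all 100 | √(30/30) = 1.00 | √(40/30) = 1.155 | √(48/30) = 1.265 |

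For example, with 52 earlier patients and k = 18, known remissions are 52 + 48 = 100 and evaluable ones are 52 × 30/48 + 48 = 80.5.

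**4. New patients.** Let each visit be missed independently with probability p (assumed). The share of remissions falling outside the window is:
- spacing equal to the window: 1 − (1−p)² = 0.19, 0.28, 0.44 at p = 0.10, 0.15, 0.25;
- spacing half the window: 1 − (1−p)²(1+2p) = 0.03, 0.06, 0.16.

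Half-window spacing is what Section 4 recommends, both for the primary outcome near normalization (2 weeks against 4) and for the later outcomes (4 weeks against 8). Spacing equal to the window is the longest routine interval in the Schedule of Events for the later outcomes.

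A simulation of the later outcomes assumed a median of 300 days, 25%/15% of visits missed on phlebotomy/hydroxychloroquine, a 62:38 split and a 728-day maximum. Exclusion was compared with midpoint-dated Cox:
- 4-week spacing: about 79% of participants evaluable, SE about 8% larger;
- 8-week spacing: about 62% evaluable, SE about 16-21% larger.

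**5. Direction of bias.** The primary outcome was simulated with no true treatment difference. Assumptions: lognormal times, median 200 days, log-SD 0.55; visits every 14 days; 28-day window; missed visits calibrated to 17 and 13 evaluable under arm splits of 28/20, 30/18 and 32/16; k = 10 or 18. HR is hydroxychloroquine v phlebotomy.

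| Rule for out-of-window remissions | HR (true 1.0) | Median, days (true 200) |
|---|---|---|
| Excluded | 0.99-1.07 | 210-224 |
| Event at first normal test | 0.99-1.10 | 210-224 |
| Censored at last abnormal test | 1.01-1.43 | 210-266 |
| Event at midpoint | 0.99-1.01 | 203 |
| Interval-censored model | 0.99-1.01 | not tabulated |

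Midpoint and interval-censored SEs were nearly the same (0.205-0.238 v 0.209-0.241).

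A separate simulation used Weibull times with a median of 28 weeks and 60%/40% of visits missed. It gave 0.97 for exclusion, 1.10 for first normal, 1.63 for censoring and 1.01 for midpoint. With 50% missed in both arms, every rule gave about 1.0.

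**The case against.** - **The windows are only a performance measure.** Section 4.G does give them that role, and they suit it. But Section 4 also makes them the condition for an evaluable time, and the interim analysed only the 30 evaluable patients. Nothing limits them to monitoring.
- **The visit rules already solve this.** In part. The recommended spacing is half the window for the primary outcome near normalization and for the later outcomes, and longer gaps call for a prior review of results. A reader of the Schedule of Events might infer that 8-week spacing is the norm and that about 40% of later-outcome times will be lost. The documents do not support that: 8 weeks is the permitted extreme. Equally, the 4-week spacing is a recommendation, and closer visits cannot repair data already collected on the earlier patients.
- **The interim loss may not be out-of-window remission.** This stands. A reader might infer from 30 of 48 that 37.5% of remissions fell outside the window. That is only an upper bound, and the Figure 2 caption permits zero. The text also does not say that the interim applied the 4-week rule, or give the loss by arm.
- **The large bias comes from a rule nobody proposed.** Also fair. Hazard ratios of 1.43 or 1.63 arise only from censoring known remissions at the last abnormal test, under assumed miss rates. The plan is silent on this rule; it does not adopt it. The simulated exclusion also kept never-normal patients as censored, whereas the interim analysed only evaluable patients.
- **The analysis is descriptive.** So no confirmatory test fails. The estimates still need a defined event time.

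**Conclusion.** The conflict is real and worth correcting, at moderate size. Sections 4 and 4.G define evaluability by a window, 4.R includes all treated patients, and no section says how a remission seen outside the window is dated.

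Exclusion costs 0-12% in the SE of the log hazard ratio if only the earlier patients are affected. The figure of 26% needs all 18 interim losses to be out-of-window remissions and the same loss to continue in all 100, which assumes that the closer visits achieve nothing. For new patients' later outcomes, the cost is about 8% at the recommended spacing and 16-21% at the permitted extreme, under the assumed miss rates.

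The bias results show direction only. With unequal missed visits, exclusion and first-normal dating both shift the hazard ratio slightly and lengthen the times, and neither ranks clearly above the other. Censoring known remissions shifts it most; midpoint dating is close to unbiased. A reader might conclude that the treatment comparison is already biased. The documents do not show that, because loss by arm is not reported and the rule has not been chosen.

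**What to change.** Add one paragraph to Section 4.R:

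1. Analyse every participant who starts treatment on the interval from the last abnormal test (exclusive) to the first normal test (inclusive). If no normal result is seen on first treatment, right-censor at the last abnormal test.
2. Use either Cox with midpoint dating or an interval-censored proportional hazards model as primary and the other as a check. They perform about equally; what matters is naming one. Apply this to the primary outcome and the three later porphyrin outcomes.
3. Keep the 4- and 8-week windows as the visit-performance measure of Section 4.G and as a sensitivity analysis restricted to in-window times.
4. Report by arm the numbers evaluable, remitted outside the window and never normal.

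The cost is that paragraph and one extra model; the test dates and results are already collected. Both models assume that visit timing is non-informative given the observed data. The noncompliance days recorded under Section 4 allow a secondary look at this, but only that, because a missed phlebotomy is also missed treatment. The change does not address non-random treatment assignment or treatment switches.
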